# 4.8. Data Collection

The electronic data systems of both dialysis provider organizations contain highly detailed clinical and treatment-related information from every dialysis treatment as well as the results of laboratory tests and hospitalization dates. Both provider organizations maintain these data in central data warehouses. For the TiME Trial, a pre-specified subset of data elements will be extracted from the central data warehouses and transferred to the DCC database at scheduled intervals. No laboratory studies will be performed specifically for the trial. While standard outpatient dialysis unit procedures using currently approved dialysis devices (Fresenius 2008K, 2008T, 2008H Series; Braun Dialog Series; Gambro Phoenix System) will be used in the trial, neither dialysis provider has the capability to track the type of device or machine characteristics used for individual treatments.

The following data elements will be obtained from clinical care data for all trial participants at the indicated frequency:

### Demographic and Comorbidity Data: all at study entry

- 1. Age
- 2. Sex
- 3. Weight
- 4. Height
- 5. Race
- 6. Ethnicity
- 7. Co-morbid illnesses noted on admission to the dialysis facility (ICD-9/10 codes)
- 8. Cause of end-stage renal disease
- 9. Extremity amputation present on admission to the dialysis facility

#### Dialysis treatment data

- 1. Session length (delivered): every session
- 2. Pre-dialysis weight: every session
- 3. Post-dialysis weight: every session
- 4. Pre-dialysis systolic and diastolic blood pressure: every session
- 5. Post-dialysis systolic and diastolic blood pressure: every session
- 7. Vascular access type (presence or absence of catheter): once per month

#### Adherence data

- 1. Prescribed dialysis session duration: every session
- 2. Delivered dialysis session duration: every session

#### Health-Related Quality of Life

1. KDQOL™36: each of 5 component summary scores annually

#### Laboratory Data: once per month

In alignment with usual practice, the following laboratory test results will be made available to the DCC by electronic data transfer once per month. It is expected that periodically some lab results will be missing and that repeated lab values will be present.

- 1. Pre-dialysis blood urea nitrogen
- 2. Post-dialysis blood urea nitrogen
- 3. Hemoglobin
- 4. White blood count
- 5. Albumin
- 6. Creatinine
- 7. Sodium
- 8. Potassium
- 9. Bicarbonate
- 10. Chloride
- 11. Calcium
- 12. Phosphorus
- 13. Glucose

#### Laboratory Data: once every 3 months

1. Intact parathyroid hormone

#### Hospitalizations dates: all

#### Status Change: all

- 1. Date of transfer to another dialysis facility
- 2. Date of kidney transplantation
- 3. Date of transfer to peritoneal dialysis
- 4. Date of withdrawal from dialysis
- 5. Date of death

#### 4.9. Participant Timeline

Participants will be followed for 3 years.

# 5. Trial Implementation

All of the TiME Trial processes will be described in detail in the Manual of Procedures (MOP). The MOP will include trial activities occurring at the dialysis facilities, dialysis provider organization data warehouses, and the DCC. The DCC is responsible for maintaining the manual and any associated documents and ensure that all relevant collaborators are informed about study procedures.

# 5.1. Centralization of Research Activities

One of the innovative aspects of the TiME trial is the reliance on centralized research personnel rather than local study staff. This model is possible because of the infrastructure of the dialysis provider organizations, and is necessary because dialysis unit staff members at the large number of participating facilities will not be engaged in the research. The project managers and the IT personnel from the dialysis provider organizations will work closely with the DCC to implement the trial and extract the specified data elements from existing data acquired through routine clinical practice. Most of the direct interfacing between the TiME Trial Study Group and participating dialysis units will be performed by the research personnel of the dialysis provider organizations. The DCC project manager will team with each dialysis provider organization project manager who, in turn, will initiate the dialysis facilities into the trial. Dialysis facilities will be enrolled and activated in stages such that problems can be identified early after the trial begins and solutions can be applied uniformly across units. Steady communication between project managers at the dialysis provider organization and the research team at the DCC will be required to ensure that standard operating procedures for the trial are used at all dialysis facilities.

# 5.2. Facility Selection

Each dialysis provider organization will identify dialysis facilities within the respective organizations that meet the eligibility criteria and are interested in participating in the TiME Trial. Effort will be made to have broad geographical representation within the United States although there will not be strict distribution requirements. Characteristics of facilities that will be incorporated into prioritization include the anticipated number of patients initiating dialysis (goal of 12 - 20 per year), distribution of dialysis session durations during the past 6 months, and capacity to accommodate the Intervention arm session duration. Preference will be given to dialysis facilities with median dialysis session duration of  $\leq 3.5$  hours in order to achieve separation between the randomized treatment groups.

The medical directors, nephrologists, clinical leadership, and facility administrators for potentially eligible facilities will be invited to learn more about the TiME Trial through educational materials developed and delivered by the TiME Trial Study Group. The leadership teams of interested dialysis facilities will be asked to provide affirmation that the medical director(s), facility administrator (or equivalent), nursing director (or equivalent), and admitting

nephrologists are willing to implement the TiME Trial intervention should the facility be randomized to the Intervention arm. After a facility has joined the TiME Trial, if the facility is randomized to the Intervention arm, formal approval of adoption of the intervention by its governing body will be required.

#### 5.3. Participant Enrollment

#### 5.3.1. Waiver of Informed Consent

The TiME Trial will be conducted under a waiver of the requirement for informed consent based on the following criteria set forth by the Federal Policy for the Protection of Human Subjects (the "Common Rule"):

- 1. The research involves no more than minimal risk to subjects.
- 2. The waiver will not adversely affect the rights and welfare of the subjects.
- 3. To the extent possible, the subjects will be provided with pertinent information after participating in the trial.
- 4. The research cannot be practicably conducted without a waiver of the requirement for informed consent.

The risk to subjects of participating in the TiME Trial is no more than minimal :

- a) the intervention consists of a dialysis session duration that is within the range of usual care administered in the United States as well as in many other countries;
- b) there are not anticipated safety concerns related to dialysis sessions of 4.25 hours; and
- c) identifying information is not transmitted to the Data Coordinating Center.

The waiver of the requirement for informed consent will not adversely affect the rights and welfare of the subjects because

- a) patients initiating dialysis treatment at a participating facility will be provided information about the trial at the time they initiate dialysis,
- b) dialysis session duration will be prescribed by a participant's treating nephrologist with opportunity for individualization of the prescription based on other considerations including patient input;
- c) patients will be provided with an opportunity to opt out of trial participation; and
- d) participant confidentiality will be protected.

To the extent possible, subjects will be provided pertinent information about the findings from the trial after participating.

Dissemination of pertinent information can be accomplished by distributing information documents at participating facilities after the trial is over.

The research question cannot be practicably answered without a waiver of informed consent.

A major objective of the trial is to evaluate effectiveness of the intervention for the overall population of patients receiving maintenance hemodialysis rather than to evaluate efficacy of the intervention for a selected, non-representative subset. Because the randomized treatment assignment for the dialysis facility will be determined before patients are enrolled, a requirement for patient-level informed consent would likely result in important differences in the characteristics of participants in the two treatment groups (intervention patients would be those who *a priori* are interested in having longer dialysis sessions and the usual care cohort would be "all comers"). These differences would substantially undermine the objectives of the TiME Trial.

#### **Patient Options**

Patients initiating dialysis will be informed about the TiME Trial when they are admitted to a participating dialysis facility or shortly thereafter. A brief "information sheet" will be given to the patient by the dialysis facility staff. The information sheet describes the purpose of the trial and what participation involves. The content differs for Intervention facilities and Usual Care facilities. The information sheet for both types of facilities contains a toll-free telephone number to allow the potential participant to obtain more detailed information about the trial if desired and to opt-out of participation if desired. Trained research staff at the dialysis provider organizations will respond to these telephone calls, provide additional information requested by the potential participant, and inform the dialysis provider organization information technology team about any patients who opt out of the transmission of their data to the DCC.

#### 5.3.2. Waiver of HIPAA Authorization

The TiME Trial will be conducted with a waiver of HIPAA authorization. Justification for waiving HIPAA authorization is based on the following factors:

1. The researchers require access to protected health information (PHI) in order to conduct the research. The only PHI that will be transmitted from the clinical data warehouses of the dialysis providers to the DCC is a limited dataset comprised of dates of dialysis sessions, death, hospitalizations, transplantation, and transfer out of a participating hemodialysis facility. Dates of dialysis sessions are needed to evaluate adherence to the intervention, to determine whether adherence is maintained over time, and to evaluate separation in treatment duration between treatment groups throughout the duration of the trial. The members of the TiME Trial research team within the dialysis provider organizations (who are employees of the covered entities) will require access to PHI in order to implement the research protocol (e.g., for assigning unique identification codes to participants, for monitoring dialysis facility adherence to the intervention and for other communication with dialysis facilities). No PHI other than dates will be distributed outside the individual provider organizations. The identity or location of dialysis facilities is sufficiently large

(approximately 400) that, without a link between participants and dialysis facilities, it is extremely unlikely that an individual could be identified from dates transmitted to the DCC.

- 2. The research cannot be practicably conducted without the waiver. The TiME Trial is designed to evaluate effectiveness of the intervention for the broad population of patients treated with maintenance hemodialysis rather than to assess efficacy of the intervention for a selected subset of patients. This trial is being conducted within a health care delivery setting at hundreds of facilities with routine dialysis care delivered by physicians, nurses and dialysis technicians. During the course of each dialysis session, information about patient status and dialysis session characteristics, obtained as part of routine care, will be used as the trial data. The health care providers at the dialysis facilities who will be generating trial data through routine clinical care are not trained in research practices and are not able to administer and explain research documents to patients such as a HIPAA waiver of authorization. Under this implementation model, obtaining authorization for disclosure of PHI from study participants is not reasonably practicable.
- 3. The use or disclosure of PHI poses no more than minimal risk to participants because a) processes will be in place to protect PHI from improper use or disclosure; b) PHI will be destroyed at the earliest possible time; and c) there will be no improper use or disclosure of PHI. Data that are transmitted to the DCC from the dialysis provider organizations will be maintained securely with access limited to authorized users. All PHI (i.e., dates) will be removed from the data set prior to any possible transfer of data from the DCC to investigators or to NIH data repositories.

The Privacy Officer at each dialysis provider organization has provided a HIPAA waiver determination to cover the work of employees with identifiable data for the purpose of creating the limited data set for research.

# 5.3.3. Participant Identification

Patients who are incident to dialysis, defined as initiation of maintenance dialysis within 120 days, and receiving care at participating dialysis facilities will be identified through the electronic data systems of the dialysis provider organizations by the TiME Trial Information Technology (IT) teams at the provider organizations. A unique research participant identifier (PID) for each participant will be generated by the dialysis provider organizations. The PID will not be related to the patient's medical record number or any other identifier. The structure of the PID will be identical between the dialysis provider organizations. The provider organizations will manage the individual PIDs and will ensure that the individual identifiers are unique across all study subjects by establishing mutually exclusive ranges of values for PIDs between the two providers. Each of the dialysis provider organizations. The keys to the unique identifiers will not be transmitted to the DCC. During the data extraction process, all personal identifiers will be replaced by the PID.

### 5.3.4. Participant Withdrawal

Participants may decide to withdraw from the study at any time. Patients who decide not to participate in the trial will have no data transmitted to the DCC. Patients who initially do not opt-out of trial participation and later elect to withdraw from the trial will have no data transmitted to the DCC after the date of withdrawal. Data transmitted to the DCC prior to withdrawal will remain in the trial database. Contact information for the research personnel from the relevant dialysis provider organization will be available at participating dialysis facilities throughout the duration of the trial to facilitate communication such as a decision to withdraw from the trial. It should be noted that participants in Intervention facilities who elect to discontinue the dialysis session duration of  $\geq$ 4.25 hours will remain as trial participants and continue to have data transmitted to the DCC unless they withdraw from the trial.

[figure not shown]
### 5.4. Data Management

### 5.4.1. Data Extraction and Transfer

During the data extraction process, all personal identifiers will be replaced by the unique research participant identifier (PID). The relevant data fields in the electronic medical records of trial participants will be tagged for export from the data warehouses of the dialysis provider organizations. (See Figure 1.) A secure file transfer protocol (sftp) site at the dialysis provider organization will be used to deliver data files. The DCC will programmatically upload these files into the DCC relational database. Automated processes will be used to review completeness of the transactions and to identify any corruption. During the initial period after the trial begins data transmission will be performed frequently in order to refine the process and identify and resolve any unanticipated problems. After all facilities are initiated and patient enrollment reaches a steady pace, the frequency of data transfer may be changed. Data and system requirements will describe the attributes of the data file exports: field, description, format, limitations, and user notes.

The dialysis provider organizations will provide a standard limited data set and an accompanying data dictionary based on the clinical data elements extracted from the dialysis provider organization data warehouse. Data extraction specialists from each of the dialysis provider organizations will query the data warehouse for the pre-determined data elements. The dialysis provider organizations will use a secure server environment for exporting data. The DCC will be responsible for ensuring the security and completeness of the data transfer and import process and the continuous security of data stored at the DCC.

The DCC central database repository will be constructed such that all imported data will retain the original structure and integrity. The transfer process will be tested according to the CRCU SOP # 9 – Data Integrity of Laboratory and Other Electronically Transferred Data. This process will ensure the secure transfer and confirmation/validation of uploaded data.

#### 5.4.2. Data Quality Procedures

Primary responsibility for data quality will reside with the data warehouse teams of the dialysis provider organizations. For both organizations, it is routine practice to regularly transmit data for inclusion in their central data warehouses. The data warehouse teams have processes to ensure that data are captured appropriately from the various originating facilities. The data extracted and transmitted from these central warehouses to the DCC is expected to be an accurate representation of the source data collected at each dialysis facility. The DCC will utilize a module to ensure that records transmitted from the central warehouse are accurately incorporated into the trial database. This module, at a minimum, will verify expected record counts and examine anomalous data based on expected data characteristics as defined by the TiME Trial study group. Data quality standards and processes for confirming missing data will be developed by the DCC in collaboration with the research teams at the dialysis provider organizations.

The clinical systems within the dialysis provider organizations are constructed with data restrictions and checks at the point of data entry for most of the primary data elements. Additional restrictions and quality checks exist at the transfer of data from the clinical system to the data warehouse. Automated measures are in place to reasonably ensure that the nightly data load process is successful and complete. If the process fails to run to completion, troubleshooting is done to identify and resolve the issue, and the process is resumed to completion. Additional quality assurance work is performed by end data users within the dialysis provider organizations as they analyze and report the data for operational purposes. These measures ensure that the database is an accurate representation of the source data collected at each dialysis clinic.

Clinical research activities at the DCC are performed in accordance with a set of standard operating procedures (SOPs) that have been implemented to promote compliance with applicable human subject protection regulations and guidelines. These SOPs are reviewed and renewed every two years. The SOP which applies to the electronic health record data

transmitted from the dialysis provider organizations describes requirements for ensuring that the integrity of electronically supplied data is maintained during the transfer and download process. It describes a systematic process of data and transfer method definition, use of scanning software to detect file corruption, encryption techniques, discrepancy management, process testing, validation procedures and documentation.

### 5.4.3. Data Security

The data management system is designed to prevent unauthorized access to trial data and to prevent data loss due to equipment failure or catastrophic events. This is accomplished through user account management, user privilege assignment, data loss prevention (database backup), computer systems validation, performance monitoring, and Data Management System change management. User access will be controlled by assignment of confidential usernames, passwords and role assignment. The system will meet the applicable Federal regulatory requirements and those described in the E6 Good Clinical Practice Guidelines to ensure the confidentiality of trial subjects.

Data are transmitted over secure connections, authenticated by the use of digital certificates and encrypted during transmission via the Internet to the DCC using secure FTP technology.

# 6. Sample Size and Analysis Plan

#### 6.1. Analysis Population

In current practice dialysis prescriptions are typically written to target urea removal. For this reason there is usually a strong association between prescribed dialysis time and estimated urea distribution volume or total body water volume (V) which usually averages 50% in women

Estimated body water	Median Treatment						
volume V(L)	Time (min)						
< 27.5	185						
27.5-32.5	206						
32.5-37.5	211						
37.5-40	213						
40-42.5	224						
> 42.5	235						

Table 1.	Treatment time and body	v water volume
		,

and 60% in men. A detailed analysis of 2,922 patients on dialysis  $\leq$ 3 years in the Renal Research Institute database in January 2012, demonstrates the expected association between treatment time and V (**Table 1**). Thus, one can foresee that for most patients with V >42.5 L, the prescribed dialysis times will be close to 4 hours, even when such

patients are receiving their initial prescriptions in a Usual Care rather than Intervention dialysis unit. Hence, for such larger patients, the times prescribed in intervention units are not expected to differ importantly

from controls.

Analysis of the same Renal Research Institute data sample suggests that about 35% of enrolling patients will have V values greater than 42.5 L and thus unlikely to be meaningfully participating

in the "time" prolongation intervention. Accordingly, the direct effects of the TiME Trial intervention will be evaluated in the *Primary Treatment Assessment Population*, which will consist of those patients with V (estimated from sex, age, and entry weight and height) ≤42.5 L.

In addition to the direct effects of treatment time, indirect effects of being enrolled in an Intervention facility versus a Usual Care facility are also possible. For example, assignment of a given dialysis facility to the Intervention group may lead to changes in unit practices that are unrelated to dialysis time but that may still affect patient outcomes. The *Extended Population* will consist of all patients in the trial and will be used to evaluate the combined direct and indirect effects of the cluster-administered intervention.

### 6.2. Sample Size

The sample size calculation is based on the comparison of mortality rates between the Intervention and Usual Care arms in the primary treatment assessment population (participants with body water volume ≤42L). The sample size requirements depend on the following factors: the minimum clinically important effect size, the mortality rate among incident patients (patients who have initiated dialysis within the past 120 days), the annual rate of loss to followup, type one error rate, and desired power. Since randomization for this trial will be at the level of the dialysis facility rather than at the patient level, the sample size also depends on the average number of participants enrolled within each dialysis facility and the intra-class correlation coefficient (ICC) (i.e., the correlation between two participants from the same dialysis facility, which describes the extent of similarity of mortality risk between two participants from the same dialysis facility).

Data from the two dialysis provider organizations from January 2011 to May 2012 suggests an overall mortality rate of 18% per year among incident patients. Other assumptions include a loss to follow-up rate of 5% per year. Loss to follow-up is expected to occur because of kidney transplantation, conversion from hemodialysis to peritoneal dialysis, and transfer to dialysis facilities belonging to a different dialysis provider organization. Based on data provided by both dialysis provider organizations, an ICC for mortality of 0.03 is expected. Based on the number of incident patients per facility at the two provider organizations, the average cluster size is expected to be 16, and it is expected that an average of approximately 10 (63%) of these patients will belong to the primary treatment assessment population.

**Table 2** shows sample size requirements under different scenarios based on an enrollment period of one year and a total study duration of three years. For the primary analysis, the desired detectable hazard ratio for mortality risk is 0.85 comparing the Intervention arm to the Usual Care arm in the primary treatment assessment population. To achieve 80% power with two-sided alpha level of 0.05, the trial requires 402 dialysis facilities (201 in each randomization arm) and a total of 6432 patients (of whom 4020 belong to the primary treatment assessment

population), assuming an ICC of 0.03. With this sample size the trial will also have 80% power to detect a HR of 0.88 in the extended population with a two-sided alpha level of 0.05.

Hazard Ratio	Intra-class Correlation Coefficient	Number of Dialysis Facilities	Sample Size for Primary Assessment Population	Total Sample Size
0.9	0.04	1038	10380	16608
	0.03	970	9700	15520
	0.02	902	9000	14432
0.85	0.04	432	4320	6912
	0.03	402	4020	6432
	0.02	374	3740	5984
0.8	0.04	230	2300	3680
	0.03	216	2160	3456
	0.02	200	2000	3200

Table 2.	Sample Size	Requirement
----------	-------------	-------------

For the secondary outcome of hospitalization, a hospitalization rate of at least one per patient per year is expected. Conservatively estimating the minimum detectable effect size using only the first hospitalization, and assuming an ICC of 0.03, the study has 80% power to detect a hospitalization risk ratio of 0.90 in the primary treatment assessment population and 0.92 in the extended population. For the quality of life outcome, estimating, based on data from the HEMO trial, that the standard deviation of the change of the Physical Health Composite is approximately 10 units from baseline to year one, and assuming that 50% of the participants will complete the KDQOL™36, the study has 80% power to detect a difference of 1.4 for the change in the physical composite score (PCS) or mental composite score (MCS) in the primary efficacy population and a mean difference of 1.1 in the extended population. In repeated measures analyses, the actual minimum detectable effect size will be even smaller because quality of life will be assessed once per year during the follow-up period.

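### The 80% power for HR 0.88 in the extended population rests on the design effect for 10 patients per facility; at the stated 16 per facility it is about 74%, and the hazard ratio detectable with 80% power is 0.87

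*Combined protocol and SAP*

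**What the plan says.** Protocol section 6.2 sizes the trial on mortality in the primary treatment assessment population: "the trial requires 402 dialysis facilities (201 in each randomization arm) and a total of 6432 patients (of whom 4020 belong to the primary" population), for 80% power at HR 0.85 with two-sided alpha 0.05. The clustering inputs are in the same section: "an ICC for mortality of 0.03 is expected", and "the average cluster size is expected to be 16, and it is expected that an average of approximately 10 (63%) of these patients" fall in the primary population.

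Section 6.1 defines the extended population as every patient in the trial. For that population section 6.2 adds: "With this sample size the trial will also have 80% power to detect a HR of 0.88 in the extended population", again at two-sided 0.05. It then gives parallel detectable effects for the secondary outcomes: a "hospitalization risk ratio of 0.90 in the primary treatment assessment population and 0.92 in the extended population", and differences in quality-of-life change of 1.4 (primary) and 1.1 (extended).

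Section 6.2.1 and Table 2R redo the power for 256 facilities, larger and unequal clusters, 10% annual loss and ICC 0.012 or 0.015, but only for HR 0.85 in the primary population. SAP section 3.1 likewise mentions power only for HR 0.85. Neither document gives a revised figure for the extended population.

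**The concern.** In a cluster-randomized trial, adding patients to the same facilities also raises the design effect. Going from the primary to the extended population raises the count per facility from 10 to 16, so the information gain is less than the ratio of the patient numbers. The stated HR of 0.88 appears to take the full ratio.

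Mortality in the extended population is a planned secondary analysis (protocol 6.3, SAP 4.3). A reader judging a null result there would use the 80% figure as the benchmark for what the design could have detected. The primary analysis and the facility count are not at stake.

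**Working it through.** **Inputs.** From protocol 6.2: 402 facilities; 6,432 patients in total, 4,020 in the primary population; 16 and 10 per facility; ICC 0.03; two-sided alpha 0.05; 18% annual mortality; 5% annual loss; 1 year of enrolment, 3 years in total. Allocation is 1:1 (section 4.4).

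**Which design effect Table 2 uses.** With DE = 1 + (m − 1) × ICC and m = 10, facilities divided by DE should be constant within each hazard ratio. For ICC 0.04, 0.03 and 0.02:
- HR 0.90: 1038/1.36 = 763; 970/1.27 = 764; 902/1.18 = 764
- HR 0.85: 432/1.36 = 318; 402/1.27 = 317; 374/1.18 = 317
- HR 0.80: 230/1.36 = 169; 216/1.27 = 170; 200/1.18 = 169

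With m = 16 the HR 0.85 rows give 270, 277 and 288, which is not constant. The primary calculation therefore uses m = 10 and DE = 1.27.

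**Anchor on the plan's primary result.** Schoenfeld's formula is power = Φ(√(events/4) × |ln HR| − 1.96), with effective events = N × P(death) / DE. The stated mortality, loss, enrolment and duration give P(death) = 0.3675 and 411 facilities, 2.2% above the stated 402. Setting P(death) = 0.3755 gives 402 exactly (4,020 × 0.3755 / 1.27 = 1,189 effective events), and I use that value.

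**Extended population, HR 0.88, N = 6,432, |ln 0.88| = 0.1278.**
- DE 1.27 (m = 10): 1,902 effective events; Φ(2.787 − 1.96) = 79.6%. This reproduces the stated 80%.
- DE 1.45 (m = 16): 1,666 effective events; Φ(2.609 − 1.96) = 74.2%. With the uncalibrated P(death) it is 73.3%.

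**Detectable HR, without an event rate.** The ratio of effective sample sizes, extended to primary, is (6,432/1.45) / (4,020/1.27) = 1.401. The HR with 80% power is exp(ln 0.85 / √1.401) = 0.872. Reusing 1.27 makes the ratio 1.60 and the HR exp(ln 0.85 / √1.60) = 0.879, the stated 0.88. Since 0.872 rounds to 0.87, rounding does not explain the difference. At m = 16, a design effect of 1.27 would need ICC = 0.27/15 = 0.018, not 0.03.

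**Parallel figures.**
- Hospitalization: exp(ln 0.90 / √1.60) = 0.920 with DE 1.27 reused; exp(ln 0.90 / √1.401) = 0.915 with DE 1.45. But 0.90 is itself a rounded result. A primary ratio between 0.9002 and 0.905 prints as 0.90 and gives 0.915 to 0.919 with DE 1.45, which prints as 0.92.
- Quality of life (SD 10, 50% completion): difference = 2.8016 × 2 × 10 × √(DE / completers). With DE 1.27 this is 1.41 (2,010 completers) and 1.11 (3,216), matching the stated 1.4 and 1.1. With DE 1.45 the extended figure is 1.19. With only completers counted in the cluster (m = 8, DE 1.21) it is 1.09, which also prints as 1.1, although the matching primary figure (m = 5, DE 1.12) is 1.32 rather than 1.4.

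**Revised design (256 facilities).** For unequal clusters, DE = 1 + ((CV² + 1) × m − 1) × ICC. With 10% loss and 36/54 months, P(death) = 0.381, and this formula reproduces all eight revised rows of Table 2R within 2 points. For all patients m = 6,880/256 = 26.9. The documents give a cluster-size SD only for the primary population (10 or 16), so the all-patient SD is an assumption. Power at HR 0.88, for ICC 0.015 and 0.012:
- SD 10: 78% and 80%
- SD 16: 75% and 78%
- SD 25.6 (16 × 1.6): 70% and 73%

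Reading 18% and 10% as hazard rates gives P(death) of about 0.357. That fits Table 2R less well and lowers the smallest cell to 67%. The range is therefore roughly 67% to 80%. Using the 6,800 printed in Table 2R instead of 6,880 moves these values by less than one point.

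**The case against.** The protocol does not print the design effect behind the extended-population figure, so reuse of 1.27 is an inference. The correction moves the detectable HR by only 0.008, in a population that does not set the sample size, and results will be reported with a confidence interval. All of this is fair and limits the point to a minor one. It does not rescue the figure: the section's own 16 per facility and ICC 0.03 do not give 80% at HR 0.88.

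A reader might also infer four stronger things, which the documents do not support:
- **That the hospitalization ratio of 0.92 is shown to be wrong.** It is not, because rounding of the primary 0.90 leaves the printed pair compatible with 16 per facility.
- **That the quality-of-life figure is likewise proven wrong.** The pair fits DE 1.27 best, but no ICC is stated for quality of life and the treatment of non-completers is open.
- **That HR 0.88 contradicts the premise in section 6.1 that for larger patients "the times prescribed in intervention units are not expected to differ importantly" from controls.** HR 0.85 in 62.5% of patients and 1.0 in the rest would give exp(0.625 × ln 0.85) = 0.903. But a detectable HR is not a predicted one, and section 6.1 assigns the extended population to the combined direct and indirect effects. This is at most an optional scenario.
- **That the sentence wrongly ignores the 256 facilities.** It refers to the original sample size. The missing update belongs to section 6.2.1 and is an omission.

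**Conclusion.** The point holds as a minor arithmetic correction. Under the original assumptions in section 6.2, power at HR 0.88 in the extended population is about 74%, not 80%, and the HR with 80% power is about 0.87. This rests on the standard design effect, which Table 2 follows in all nine rows, on the stated 16 per facility taken as equal cluster sizes, and on ICC 0.03. The detectable HR does not depend on the assumed death rate if the event probability is the same in both populations.

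For the revised design no single figure can be given. The lower ICC offsets the larger clusters in part, and the result turns on an all-patient cluster-size SD that the documents do not state. The primary sample size, the interim boundary and the analysis methods are unaffected.

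**What to change.** In protocol 6.2, restate the extended-population mortality sentence as 80% power for HR 0.87 (about 74% at HR 0.88), and name the design effect used (1.45, for 16 per facility). Recheck the extended-population figures for hospitalization (0.92) and quality of life (1.1) with the 16-per-facility design effect from the unrounded working, and change them only if that working requires it.

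If section 6.2.1 is revised, add an extended-population power for 256 facilities and 6,880 patients, stating the all-patient cluster-size SD and the ICC assumed.

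The cost is a few words and one rerun of an existing calculation, with slightly less favourable stated figures. Nothing changes in design, enrolment or analysis.
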